Other baseline variables may also be assessed if there is clinical or biological justification or an imbalance is observed between the treatment arms. The purpose of the subgroup analyses is to assess the consistency of treatment effect across expected prognostic factors.

No adjustment to the significance level for testing will be made since the subgroup analysis may only be supportive of the primary analysis of DFS. For each subgroup level, the HR and 95% CI will be calculated from a single Cox PH model that contains a term for treatment, the subgroup covariate of interest, and the treatment by subgroup interaction term. The HR will be

obtained for each level of the subgroup from this model. The Cox models will be fitted using SAS® PROC PHREG with the Efron method to control for ties.

These HRs and the associated 95% CIs will be summarised and presented on a forest plot, along with the results of the overall population and non-IBs.

If there are too few events available for a meaningful analysis of a particular subgroup (it is not considered appropriate to present analyses where there are less than 20 events per level in a subgroup), the relationship between that subgroup and DFS will not be formally analysed. In this case, only descriptive summaries will be provided.

4.3.7.2. Secondary Outcomes

Analysis of DFS Rate

DFS rate data will be analysed using the same model as for the primary analysis of DFS.

KM plots will be produced to assess if recurrence rates have reached an apparent plateau. Estimates of DFS rate at 6 months, 12 months, 18 months, 24 months, 36 months, 48 months and 60 months obtained from the plot will be presented for each arm. If the shape of the DFS curve suggests a plateau, a cure rate model will also be fitted.

Analysis of Overall Survival

Survival Status will be summarised in terms of those who have died or censored whereby patients may be alive and ongoing in the study or discontinued the study prior to death. OS data will be analysed using the same methodology and model as for the analysis of DFS (with the exception that the sensitivity, subgroup and exploratory analyses will not be performed), provided there are sufficient events available for a meaningful analysis (i.e. >20 deaths [if not, descriptive summaries will be provided]).

OS rate will be estimated at 2, 3 and 5 years will be estimated for each arm from a KM plot of OS at the time of the primary analysis. This will be estimated for non-IBs and overall.

If more mature data on OS is required, then it may be analysed at a later timepoint.

Additional exploratory analysis of OS adjusting for the impact of treatment switching may be performed** if patients randomised to placebo subsequently receive a T790M directed EGFR-TKI. Methods such as Rank Preserving Structural Failure Time (RPSFT) (Robins & Tsiatis, 1991), Inverse Probability of Censoring Weighting (IPCW) (Robins & Finkelstein, 2000) and other methods in development may be explored. The decision to adjust and final choice of methods will depend on the observed data and the plausibility of the underlying assumptions and the results from these analyses will be reported separately from the CSR.

** internally by AstraZeneca.

Analysis of Health-Related Quality of Life

The compliance with SF-36 will be summarised by visit.

The scores for each of the eight health domains scores and for each of the PCS and MCS measures from the SF-36 will be summarised in terms of mean score and change from baseline values at each post-baseline assessment. The responses to each of the health domain scores and summary measures will also be categorised in terms of improved, worsened, and stable at each post-baseline assessment.

The primary HRQoL outcome measures of interest are time to deterioration of the two aggregated summary scores (MCS and PCS). The probability of making a type I error (5% two-sided) will be split equally between these two analyses. Time to deterioration in the subset of patients with stage IIA-III A cancer will be analysed using a log-rank test stratified by stage (II, IIIA), mutation type (Ex19Del, L858R either alone or in combination with other EGFR mutations) and race (Asian, Non-Asian) using the Breslow approach for handling ties.

For two missed visits rule please refer to user's manual for SF-36V2 Health Survey, third edition.

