8.5.3 Analysis of health-related quality of life

The scores for each of the 8 health domain scores and for each of the physical and mental component summary measures from the SF-36 v2 will be summarised in terms of mean changes from baseline at each post-baseline assessment.

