1.3. Number of Patients

Approximately 700 patients will be randomised globally in a 1:1 ratio (AZD9291: placebo) to this study. The primary endpoint of the study is DFS based on investigator assessment. DFS will first be tested in the subset of patients with Stage IIA-III A cancer. If statistical significance is shown for DFS in the subset of patients with Stage IIA-III A cancer, then it will be tested for the overall population with the test mass split between first and second analyses.

The primary analysis of DFS will occur when approximately 247 disease recurrence events have been observed in approximately 490 patients who are in Stage IIA-III A (i.e. non-IB). If the true DFS hazard ratio (HR) for the comparison of AZD9291 versus placebo in this patient population is 0.70, 247 disease recurrence events will provide 80% power to demonstrate a statistically significant difference in DFS at a 5% two-sided significance level (translating to an improvement in median DFS from 40 months to 57 months, assuming DFS is exponentially distributed). The minimum DFS HR that would be statistically significant (i.e. $p < 0.05$, two-sided) is 0.78.

If the true DFS HR for the comparison of AZD9291 versus placebo in the overall population is 0.70, 314 disease recurrence events will provide approximately 90% power to demonstrate a statistically significant difference in DFS at a 4% two-sided significance level (translating to an improvement in median DFS from 46 months to 66 months, assuming DFS is exponentially distributed). The minimum DFS HR that would be statistically significant (i.e. $p < 0.04$, two-sided) is 0.79.

At the time of the primary analysis it is anticipated that approximately 195 OS events (28% maturity) will have occurred (assuming a median OS of 96 months for the placebo arm) in the overall population. If the true OS HR for the comparison of AZD9291 versus placebo is 0.66, 195 death events provide approximately 80% power to demonstrate a statistically significant difference at the 4% (two-sided) significance level. With 195 death events and assuming a true OS HR of 0.85 there is approximately 90% chance of observing an HR < 1.02 .

Assuming 28 months non-linear recruitment the data cut-off for the primary analysis is estimated to occur approximately 68-70 months after first patient randomised.

It is estimated that 3200 patients will be screened in order to randomise 700 patients.

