4.2.2. Multiple Testing Strategy

A single, primary analysis is planned for this study, with a further analysis performed only if there are significantly less than 70 DFS events (i.e. 63 DFS events or less) in the IB population at the time of the primary analysis. The primary endpoint of DFS and secondary endpoint of OS will be tested in the subset of patients with stage IIA-III A cancer as well as in the overall population. In order to describe the nature of the benefits of AZD9291 treatment, primary and secondary endpoints will be tested at a two-sided significance level of 5%. However, in order to strongly control the type I error at 5% two-sided level, a hierarchical testing procedure will also be employed across the primary endpoint and secondary endpoint of OS, intended for key label claims.

[figure not shown]
DFS in patients who are in Stage IIA-III A (i.e. non-IB) is tested first using the full test mass (full test mass = alpha).

DFS in the overall population will only be tested, with the test mass split between first and second analyses, if statistical significance is shown for DFS in patients who are Stage IIA-III A. OS (in both populations) will only be tested, with the test mass split between first and second analyses, if statistical significance is shown for DFS in the overall population.

Both DFS in the overall population and OS in both populations will be tested at the time of the primary analyses of DFS in patients who are Stage IIA-III A and may be tested again when at least 70 DFS events in the IB population have been observed (if there were significantly less than 70 DFS events at the primary analysis). Only a proportion of alpha will be spent at the first analyses for both endpoints to control for multiple testing.

The hierarchical testing procedure at the time of the primary analysis is shown in Figure 2. At the time of the primary analysis, DFS in patients who are in Stage IIA-III A is tested first using the full test mass of 5%. If this result is statistically significant, DFS in the overall population will be tested at 4%. If this result is statistically significant, OS in patients who are in Stage IIA-III A will be tested at 4%. If this result is statistically significant, OS in the overall population will be tested at 4%.

[figure not shown]
Figure 2 Hierarchical Testing Procedure at time of Primary Analysis

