4.3.7. Efficacy

All efficacy analyses will be performed on the FAS. Results of all statistical analyses will be presented using a 95% CI and two-sided p-value.

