7. REVISION TO MULTIPLE TESTING STRATEGY

This section supersedes earlier text regarding alpha allocation.

At the time of the scheduled IDMC meeting for safety in April 2020, the IDMC requested efficacy data. Based on the review of this data, the IDMC made the recommendation to unblind the study and complete primary reporting. Given these unplanned analyses of efficacy, the alpha allocation needs to be revised to control the type I error.

No changes will be made to the order of the hypothesis being tested.

Primary Endpoint: DFS in stage II/IIIA

The primary analysis was planned to be conducted when approximately 247 DFS events were observed in the stage II/IIIA population. This represents 50% maturity based on the planned sample size of 490 subjects.

Two unplanned interim analysis of DFS in the stage II/IIIA population were conducted at the time of observing 86 DFS events and 156 DFS events respectively. The corresponding information fractions were 0.35 and 0.63 where the final number of events would have been 247. The Lan DeMets approach that approximates the O'Brien and Fleming spending function will be used to maintain an overall 2-sided 5% type I error. Using statistical software package EAST, the following stopping boundaries are obtained and shown below in [Table 6](#).

The exact number of events, associated information fractions and 2-sided p-values will be confirmed after database lock and unblinding.

Table 6 Alpha allocation under Lan-DeMets with O'Brien-Fleming type spending function, stage II/IIIA population

Timepoint	Number of events/ information fraction/maturity	Critical value (HR)	2-sided p- value
IDMC6 (April 2019) - safety and futility review	86/0.35/18%	0.4590	0.00030
IDMC7 (April 2020) - safety review	156/0.63/33%	0.6588	0.009384
Primary planned analysis per protocol (expected Q1 2022)	247/1.0/53%	0.7763	0.04701

An exploratory DFS analysis in the stage II/IIIA population will be conducted once approximately 247 DFS events have occurred. This analysis will not be formally tested and will be considered exploratory. At this time, an exploratory analysis of DFS in the overall population will also be conducted.

DFS in the overall population

If testing of the DFS in stage II/IIIA population is statistically significant, the full 2-sided 5% alpha can be recycled forward into testing endpoints pre-specified in the hierarchical testing procedure. The next test in the hierarchical procedure is to test the DFS in the overall population.

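### The two HRQoL time-to-deterioration tests (PCS and MCS) each get a fixed 2.5%; this is valid, but a Holm step-down would keep the same 5% family-wise bound with more power on the second measure

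*SAP*

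**What the plan says.** SAP 1.1 lists health-related quality of life as a secondary objective. Most of the SF-36 output in SAP 4.3.7.2 is descriptive: mean scores, changes from baseline, and the categories improved, worsened and stable. Two tests are added. "The primary HRQoL outcome measures of interest are time to deterioration of the two aggregated summary scores (MCS and PCS"), and "The probability of making a type I error (5% two-sided) will be split equally between these two analyses". The method is given as follows: "Time to deterioration in the subset of patients with stage IIA-III A cancer will be analysed using a log-rank test stratified by stage", with mutation type and race as further strata.

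The SAP does not print 2.5%; it follows from halving 5%. The SAP does not say that alpha is passed from one measure to the other, and gives no reason for the equal split. It states no effect size, event count, power or correlation for these two tests.

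Three other places matter:

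- SAP 4.2.2 limits the strongly controlled sequence to DFS and OS: "a hierarchical testing procedure will also be employed across the primary endpoint and secondary endpoint of OS, intended for key label claims". SAP 7, which revises the alpha allocation, also deals only with DFS and OS.
- SAP 4.3.7 sets the reporting format for efficacy: "Results of all statistical analyses will be presented using a 95% CI and two-sided p-value".
- Protocol 8.5.3 plans no HRQoL test at all; the scores "will be summarised in terms of mean changes from baseline at each post-baseline assessment".

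**The concern.** An equal split with no step-down is the Bonferroni procedure. Suppose PCS gave p = 0.001 and MCS gave p = 0.03. Under the SAP, MCS is not significant. Under Holm, the smaller p-value is compared with 0.025 and passes, the other is then compared with 0.05 and also passes, and both results can be claimed within the same 5% family-wise bound.

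The sponsor already uses this principle elsewhere. In SAP 7, once DFS in stage II/IIIA is significant, "the full 2-sided 5% alpha can be recycled forward into testing endpoints pre-specified in the hierarchical testing procedure". Nothing similar is provided for PCS and MCS.

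At stake is power on whichever HRQoL measure has the larger p-value, in the only two inferential HRQoL analyses in the plan.

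**Working it through.** **Inputs from the documents.** Family alpha is 5% two-sided, there are two tests, and the split is equal (SAP 4.3.7.2).

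**Inputs that are assumptions.** Each measure has 80% power at two-sided 5%, with correlation 0, 0.5 or 0.7 between the two test statistics. The documents give no values for either.

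**Step 1: the plan's own figure.** 0.05 / 2 = 0.025 per test, and 0.025 + 0.025 = 0.05. If both nulls are true and the tests are independent, the family error is 1 − 0.975² = 0.0494. The stated 5% control is reproduced.

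**Step 2: error control under Holm.** When both nulls are true, Holm makes a false claim only if the smaller p-value is at or below 0.025, which is exactly when the equal split makes one. The family error is therefore identical: 4.94% at correlation 0, 4.65% at 0.5 and 4.30% at 0.7. When only one null is true, Holm tests it at 5% at most, so the bound holds under any dependence.

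**Step 3: power at correlation 0.** The cut-offs are 2.2414 (2.5%) and 1.9600 (5%). A test with 80% power at 5% has mean 1.9600 + 0.8416 = 2.8016.

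- Power at 2.5%: Φ(2.8016 − 2.2414) = Φ(0.5602) = 0.712.
- Probability that p lies between 0.025 and 0.05: 0.800 − 0.712 = 0.088.
- Per measure under Holm: 0.712 + 0.088 × 0.712 = 0.775.
- Both significant, equal split: 0.712² = 0.507.
- Both significant, Holm: 0.800² − 0.088² = 0.632.
- At least one significant, either method: 1 − (1 − 0.712)² = 0.917.

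**Step 4: with correlation** (bivariate normal probabilities, two-sided).

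| Correlation | Per measure: split → Holm | Both: split → Holm | At least one, either method |
|---|---|---|---|
| 0 | 71.2% → 77.5% | 50.7% → 63.2% | 91.7% |
| 0.5 | 71.2% → 76.5% | 57.2% → 67.7% | 85.3% |
| 0.7 | 71.2% → 76.0% | 60.5% → 70.0% | 82.0% |

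**Step 5: sensitivity to the assumed power.**

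- With 80% power at 2.5% instead, the chance that both are significant goes from 64.0% to 75.1% (correlation 0), 68.7% to 77.8% (0.5) and 72.9% to 80.4% (0.8).
- With one measure at 90% and the other at 50% (both at 2.5%), the weaker one rises to about 60% or 61%.
- With both at 30%, each gains 3 to 4 points.

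**Step 6: what Holm gives up.** If one measure has no effect and the other is almost certain to be rejected, the chance of a false claim on the null measure is 2.5% under the split and 5.0% under Holm. If the other measure has only the power assumed in Step 3 (71.2% at the 2.5% level) and the tests are independent, the risk under Holm is 0.025 + 0.025 × 0.712 = 0.043.

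**The case against.** The strongest answer is that an equal, pre-specified split is a valid and conservative choice, and that preferring Holm is a choice between two sound methods. That stands: there is no contradiction, bias or loss of error control in the SAP.

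A reader might infer more, namely that the SAP gives up power for nothing, with no gain in error control. The documents do not support that reading:

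- The split protects each measure separately at 2.5%. Holm lets that risk reach 5% for a null measure once the other has been rejected. Both respect the 5% family bound, but the protection of each measure differs.
- The split has simple simultaneous 97.5% intervals that match the tests; Holm does not. This advantage is only potential here. SAP 4.3.7 plans 95% intervals, so an interval could exclude no effect while the test at 2.5% is not significant.
- Holm does not change the chance of at least one HRQoL success. It helps only when one p-value is at or below 0.025 and the other lies between 0.025 and 0.05.

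The consequence is also limited. HRQoL lies outside the DFS and OS sequence, no other test depends on it, and a p-value of 0.03 on the second measure would still be reported.

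Timing is the most serious practical objection. SAP 7 (edition 4.0, June 2020) still placed database lock and unblinding ahead, and scheduled every analysis due at primary reporting for that point. Protocol 8.7 (edition 6.0, August 2023) describes the study as already unblinded and reported. Moving the second threshold from 2.5% to 5% after the results are known would be a post hoc relaxation in the sponsor's favour. This objection stands in full.

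**Conclusion.** The point holds as an inexpensive efficiency gain, not as an error in the SAP. PCS and MCS are each tested at a fixed 2.5%, and Holm would keep the same 5% family-wise bound while never rejecting less.

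Under an assumed 80% power per measure at 5%, the gain is about 5 to 6 points per measure and 9 to 12 points for both measures being significant, over correlations 0 to 0.7. The direction of the gain does not depend on these assumptions; its size does, and the documents supply nothing to replace them. The consequence is modest, because the gain falls only on the measure with the larger p-value and HRQoL carries no weight in the DFS and OS sequence.

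**What to change.** If HRQoL results have not been unblinded, replace the sentence on the equal split in SAP 4.3.7.2 with:

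> PCS and MCS time to deterioration will be tested with the Holm procedure at a family-wise two-sided 5%: the smaller p-value is compared with 0.025 and, if significant, the other with 0.05.

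This is one sentence and needs no new data or analysis. The sponsor would be accepting the higher risk on a null measure and the lack of simple matching simultaneous intervals; 97.5% intervals could still be shown descriptively.

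If HRQoL results have been unblinded, as Protocol 8.7 implies, the fixed 2.5% split must stand. A Holm result could then be shown only if labelled post hoc.

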4.3.7.3. Exploratory Outcomes

Healthcare Care Resource Use

Health Care Resource Use data (i.e. the hospital admission details including type of attendance and primary symptom for admission) will be listed and presented using frequencies and percentages. The duration of admission/attendance and duration of intensive care unit (ICU)/high dependency unit (HDU) stay will be summarised using descriptive statistics, based on the FAS. It will summarised from randomisation and up to and including treatment discontinuation.

Analysis of Progression-Free Survival

Progression status at the time of analysis by treatment arm will be categorised into radiological, symptomatic, other progression or death, with reasons for censoring also summarised accordingly. PFS data will be analysed for the overall population using the same methodology and model as for the analysis of DFS with the exception that the sensitivity, subgroup and exploratory analyses will not be performed. The HR for the treatment effect together with its 95% CI will be presented. In addition, medians and Kaplan-Meier plot will be presented by treatment arm to support the analysis. It will be summarised per treatment arm, but no formal comparisons will be made. No multiplicity adjustment will be applied as this is viewed as a supportive endpoint. Time from randomisation to progression will be summarised by treatment arm.

Post-Relapse Outcomes

TFST and TSST will be summarised for the overall population using the same methodology and model as for the analysis of DFS with the exception that the sensitivity, subgroup and

exploratory analyses will not be performed. The HR for the treatment effect together with its 95% CI will be presented. In addition, medians and a Kaplan-Meier plot of the time to the start of subsequent therapy will be presented by treatment arm and the time between recurrence and starting subsequent therapy will be assessed. This will be summarised per treatment arm, but no formal comparisons will be made. No multiplicity adjustment will be applied as this is viewed as a supportive endpoint.

In patients who received a subsequent anti-cancer therapy, a summary table of first (and second) subsequent anti-cancer therapies by treatment arm will be provided, as well as response to first subsequent anti-cancer therapy by treatment arm (if available).

A summary of the number of patients prematurely censored will also be produced.

Analysis of EGFR Mutation Status Between Tumour DNA And Plasma-Derived CtDNA

Cross-tabulation summaries of the mutation status from EGFR mutation status from tumour DNA (Positive, Negative, Total) versus the mutation status from plasma-derived ctDNA (Positive, Negative, Unknown, Total) will be produced for:

- all screened patients who are evaluable (Positive, Negative) for baseline tumour mutation status
- all screened patients who are evaluable for both the baseline tumour mutation status and the recurrence mutation status

The concordance (i.e. both positive or both negative), sensitivity, specificity, positive predictive value (PPV) and negative predictive value (NPV) rates for the EGFR mutation status will be produced for subgroups of patients as mentioned above. The 95% CIs using Wilson score intervals will be presented for each of these, however if the number of patients in the subgroup is <30, then the Clopper-Pearson method (Clopper & Pearson, 1934) will be used to derive the 95% CI.

Sensitivity is defined as:

$$100 \times \frac{\text{number of patients who are EGFR positive from both tumour sample and plasma-derived}}{\text{number of patients who are EGFR positive from tumour sample}}$$

Specificity is defined as:

$$100 \times \frac{\text{number of patients who are EGFR negative from both tumour sample and plasma-derived}}{\text{number of patients who are EGFR negative from tumour sample}}$$

PPV is defined as:

$$100 \times \frac{\text{number of patients who are EGFR positive from both tumour sample and plasma-derived}}{\text{number of patients who are EGFR positive from plasma-derived}}$$

NPV is defined as:

$$100 \times \frac{\text{number of patients who are EGFR negative from both tumour sample and plasma-derived}}{\text{number of patients who are EGFR negative from plasma-derived}}$$

Analysis of Plasma-Derived ctDNA EGFR Mutation Status at Baseline Compared to Status at Disease Recurrence

Cross-tabulation summaries of the mutation status from the first plasma sample at baseline (Positive, Negative, Unknown, Total) versus the mutation status from the plasma sample taken at disease recurrence (Positive, Negative, Unknown, Total) will be presented:

- in patients from the FAS population who are evaluable for both the first plasma sample and the recurrence plasma sample

The concordance rate and its 95% CI for the EGFR mutation status of the first plasma sample versus the progression plasma sample will also be presented for groups described above.

Analysis of Time to New Brain Lesion or Death

Time to new brain lesion or death will be summarised for the stage II/IIIA and overall population using the same methodology and model as for the analysis of DFS with the exception that the sensitivity, subgroup and exploratory analyses will not be performed. An event is a recurrence with evidence of a CNS lesion or death by any cause. Patients without an event will be censored at the last evaluable disease assessment. The HR for the treatment effect together with its 95% CI will be presented. No multiplicity adjustment will be applied as this is viewed as a supportive endpoint.

